**Figure 1 Diagram of Study Design**

## **Number of Participants**

Up to 20 participants will be enrolled in a 1:1 ratio to each of the two dosing regimen orders shown in Figure 1. Of the enrolled population, at least 50% will be post-RYGB; the remainder will be post-VSG, -gastrectomy, -esophagectomy, or -Nissen fundoplication. Randomization will be stratified by type of surgery RYGB vs Others (including VSG, gastrectomy, esophagectomy, or Nissen fundoplication).

## **Rationale for Dose and Dose Regimen Selection**

The dose levels of avexitide and the dosing intervals selected for this study are based on results from the Phase 2 PREVENT study, a randomized, placebo-controlled crossover study evaluating two dosing regimens (30 mg BID and 60 mg QD) in 18 patients with diet-refractory PBH. On the basis of the strength and consistency of study results from the PREVENT trial and the safety and tolerability profile associated with avexitide exposure, we seek to conduct a preliminary analysis of use of a 90 mg total daily dose administered as 45 mg BID and 90 mg QD, as it is of our opinion that higher total daily exposure may be well-tolerated and has the potential to result in even more robust clinical outcomes.

## **STUDY POPULATION**

### **Inclusion Criteria**

Patients must meet all of the following inclusion criteria before study entry to be eligible for enrollment.

1. Able to understand the purpose and risks of the study; willing and able to adhere to scheduled visits, treatment plans, laboratory tests, procedures, and provide written informed consent
2. History of qualifying bariatric or upper-gastrointestinal surgery (RYGB, VSG, gastrectomy, esophagectomy, or Nissen fundoplication) at least 12 months prior to the start of Screening
3. Male or female, at least 18 years old (inclusive) at Visit 1 (Screening)
4. Body mass index (BMI) of up to 40 kg/m^2
5. Has stable body weight, i.e., not varying by >5% for at least 4 months prior to Visit 1 (Screening), as documented by the investigator
6. History of recurrent hypoglycemia refractory to bariatric dietary recommendations occurring after bariatric or upper-GI surgery, as documented in the medical record.
7. At least two severe hypoglycemia events from which at least one must be characterized by glucose <54 mg/dL as measured by CGM during the 14-day Run-in Period while adhering to medical nutritional therapy.
8. If female, must meet the following criteria:
  - a. Not breastfeeding or lactating
  - b. Negative urine pregnancy test result at Visit 4 (Screening) (not applicable to hysterectomized females); urine pregnancy test at Screening must be confirmed negative prior to randomization and dosing.
  - c. If of childbearing potential (including peri-menopausal women who have had a menstrual period within 1 year) must agree to use appropriate birth control (defined as a method which results in a low failure rate, i.e., less than 1% per year, when used consistently and correctly, such as implants, injectables, hormonal contraceptives, some intrauterine

contraceptive devices, sexual abstinence, tubal ligation or occlusion, or a vasectomized partner) during the entire duration of the study. Subjects must practice appropriate birth control as stated above for 4 weeks after the last dose of study drug.

- Nonchildbearing potential is defined as surgically sterile (documented hysterectomy, tubal ligation, or bilateral salpingo oophorectomy) or postmenopausal (defined as 12 months of spontaneous amenorrhea).
- 9. Has no clinically significant abnormal complete metabolic panel (CMP) as judged by the investigator. Note: CMP collected at Visit 4 unless assessed within 6 months prior to randomization.
- 10. Has no clinically significant medical condition, as judged by the investigator, at Screening

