## INVESTIGATIONAL PLAN

### Study Design

**Overview**—This is a Phase 2b, single center, open-label, cross-over study of avexitide injection in patients with surgically-induced severe, diet-refractory HH. Eligible participants must have a confirmed diagnosis of surgically-induced HH and demonstrate severe, diet refractory HH, as documented by presence of at least two severe hypoglycemia events from which at least one must be characterized by glucose <54 mg/dL as measured by CGM during the 14-day Run-in Period while adhering to medical nutritional therapy.

[figure not shown]
Eligible HH indications include hypoglycemia occurring after:

- Bariatric Surgery:
  - Roux-en-Y Gastric Bypass (RYGB) or Vertical Sleeve Gastrectomy (VSG)
- Upper-Gastrointestinal Surgery:
  - Gastrectomy, Esophagectomy, or Nissen Fundoplication

Provisionally eligible subjects will undergo a 14-day Run-In consisting of standard of care (SOC) treatment (medical nutrition therapy) with standardized mixed meal consumption and screening labs and collection of blood to test for anti-drug antibody (ADA) at the end of the 14-day SOC Run-In to confirm eligibility and establish a baseline within 90 days of randomization. Enrolled participants will be randomized to one of two 14-day avexitide dosing regimen orders (Figure 1). Doses are to be self-administered in the outpatient setting via subcutaneous (SC) injection. Throughout the study duration participants will continue to maintain SOC treatment following standard dietary guidelines for management of PBH and will be evaluated by blinded CGM, patient electronic diary (eDiary) and SMBG. At the end of Treatment Periods 1 and 2, participants will repeat baseline assessments with ADA and trough PK samples additionally drawn. At the end of Treatment Period 2, participants will return used and unused study drug vials during the safety follow-up visit.

**Study Duration**— Depending on when a patient completes the Run-In Period, the maximum anticipated time an individual patient will participate in the study will be ~120 days.

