## **STUDY CONDUCT AND ASSESSMENTS**

### **Screening Procedures**

Patients providing written informed consent will be evaluated to determine eligibility to participate in the study. An initial eligibility review will be conducted, including:

- review of medical history and concomitant medications
- review of Level 2 and Level 3 hypoglycemia event rate (<54 mg/dL by CGM or Level 3 hypoglycemia) during Run-In
- review of clinical lab results

- pregnancy testing (as applicable)

The preliminary eligibility assessments may be performed up to 90 days prior to randomization, consisting of a 14-day Baseline Run-in period during which the following items will be supplied concurrent with training:

- eDiary
- dietary guidelines (describes SOC medical nutrition therapy)
- glucometer, lancets and test strips
- Dexcom G6PRO

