### **Figure 2**

## Criteria for Evaluation

### ***Primary Efficacy Endpoint***

- The primary endpoint is the baseline-adjusted number of diurnal Level 2 hypoglycemia events (ADA, <54 mg/dL) as measured by CGM and defined as the number of events captured by CGM with glucose measures <54 mg/dL during diurnal hours (8am-10pm) within each treatment period divided by number of days for a given treatment period, then normalized to duration of 14 days. The baseline-adjusted number of diurnal Level 2 hypoglycemia events during 14 days of avexitide treatment (Treatment Periods 1 and 2) and 14 days of standard of care treatment (Run-In Period) will be calculated and examined in a mixed-effect model, including treatment, treatment sequence, treatment period, and surgery type stratum (RYGB vs. Others) as fixed effect, and subject-within-sequence as random effect. The least squares (LS) mean, the standard error (SE), the 2-sided 95% confidence interval (CI), and the p-value will be derived from the mixed-effect model for each active treatment. No multiplicity adjustment is planned, and the primary endpoint will be evaluated through the nominal p-values. P<0.05 is considered statistically significant.

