### ***Secondary Endpoints***

The secondary endpoints include the following:

- Rate of Level 2 hypoglycemia, defined as number of distinct episodes of Level 2 hypoglycemia (SMBG glucose <54 mg/dL), divided by number of days for a given treatment period, then normalized to duration of 14 days.
- Rate of Level 3 hypoglycemia (severe hypoglycemia), defined as the number of severe events during each treatment period characterized by altered mental and/or physical functioning that requires assistance from another person for recovery, divided by number of days for a given treatment period, then normalized to duration of 14 days. This applies regardless of whether a patient actually receives external assistance. Since the categorization of a severe hypoglycemia event can be subjective, particularly in cases where severe neuroglycopenic symptoms/signs occurred and external assistance was needed but was not received, all potential qualifying severe hypoglycemia events will be adjudicated by the principal investigator.
- Percent diurnal time <54 mg/dL, defined as the percentage of CGM values <54 mg/dL during daytime hours (8am-10pm) within each treatment period, normalized to 14 days.
- The magnitude of postprandial hypoglycemia, defined as the glucose nadir as measured by fingerstick glucose occurring within 3 hours of standardized liquid meal consumption. The plasma glucose nadir obtained during avexitide plus standard of care (Treatment Periods 1 and 2) will be compared to during standard of care (Run-In). Particularly, the baseline-adjusted plasma glucose nadir will be calculated for each patient and evaluated.

Secondary endpoints will be analyzed in the same manner as the primary efficacy endpoint.

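### Eligibility is decided on hypoglycemia events in the same Run-In that serves as comparator, so regression to the mean favours avexitide in each regimen-versus-Run-In comparison of CGM Level 2 events, by an unknown amount

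*Combined protocol and SAP*

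**What the plan says.** Inclusion Criteria, item 7, admits a participant only with "At least two severe hypoglycemia events from which at least one must be characterized by glucose <54 mg/dL as measured by CGM" in the 14-day Run-In. Study Design (Overview) gives the Run-In two purposes: "to confirm eligibility and establish a baseline within 90 days of randomization". The same section randomizes order only: "Enrolled participants will be randomized to one of two 14-day avexitide dosing regimen orders". There is no placebo, no untreated period after selection and no second baseline.

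Primary Efficacy Endpoint sets avexitide beside the same window: the counts on treatment and during "14 days of standard of care treatment (Run-In Period) will be calculated and examined in a mixed-effect model". The model is described as "including treatment, treatment sequence, treatment period, and surgery type stratum (RYGB vs. Others) as fixed effect", with subject-within-sequence random, and yields a p-value for each active treatment. The decision rule is: "No multiplicity adjustment is planned, and the primary endpoint will be evaluated through the nominal p-values. P<0.05 is considered statistically significant". The term *baseline-adjusted* is not defined.

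What counts as a qualifying event is not settled. Screening Procedures refers to a "review of Level 2 and Level 3 hypoglycemia event rate (<54 mg/dL by CGM or Level 3 hypoglycemia) during Run-In", whereas Secondary Endpoints ties *severe* to the Level 3 rate: "the number of severe events during each treatment period characterized by altered mental and/or physical functioning that requires assistance".

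**The concern.** A person's 14-day event count varies by chance around that person's usual rate. Admitting only people whose Run-In count reaches a threshold favours Run-Ins that happened to be high. The following periods are not selected, so the average count drifts back down without any drug effect.

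Nothing in the plan separates this drift from efficacy. Run-In is always first and always untreated, so the period term cannot separate it from treatment, and no other term represents the selection. The drift enters each regimen's comparison with Run-In, to which the plan attaches P<0.05. At stake is whether a significant fall in the primary endpoint can be read as an effect of avexitide.

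**Working it through.** **Inputs from the documents.** Threshold: two events, at least one on CGM below 54 mg/dL (criterion 7). Window: 14 days. Sample size: up to 20 (Number of Participants). Two-sided 0.05, hence 2.5% in the favourable direction (Primary Efficacy Endpoint). The documents state no event rate, SD, power or screen-failure rate, so there is no plan figure to reproduce.

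**Assumptions.** Inert drug; Poisson counts; personal rates gamma-distributed across candidates; candidate mean m of 2, 4 or 8 CGM events per 14 days.

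**Step 1, a case that can be done by hand.** Take gamma shape 1, stable personal rates and two CGM events required. Run-In counts R are then geometric:

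- Share qualifying = (m/(m+1))².
- Mean Run-In count among those admitted = m + 2.
- Expected rate given R = (R+1)·m/(m+1), so the mean next-period count = m(m+3)/(m+1).
- Fall = (m+2) − m(m+3)/(m+1) = 2/(m+1).

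| m | Qualify | Run-In | Next period | Fall |
|---|---|---|---|---|
| 2 | 44% | 4.00 | 3.33 | 0.67 (16.7%) |
| 4 | 64% | 6.00 | 5.60 | 0.40 (6.7%) |
| 8 | 79% | 10.00 | 9.78 | 0.22 (2.2%) |

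If one CGM event suffices, the fall is 1/(m+1) from a Run-In mean of m+1, a proportion of 1/(m+1)²: 11.1%, 4.0% and 1.2%.

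**Step 2, simulation over a range** (shape 1-2, with or without period-to-period variation in a person's rate, n=20, t-test on change from Run-In, two CGM events required):

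| m | Spurious fall | Favourable and significant |
|---|---|---|
| 2 | 17-27% | about 25-37% |
| 4 | 7-13% | 9-11% |
| 8 | 2-5% | 4-5% |

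If one CGM event suffices, the fall is 1-16% and the favourable rate 3-13% across the three means. With other variability assumptions (between-person CV 0.5 or 1.0, period CV 0 or 0.5) and two events required, mean 2 gives 17-33% and 23-48%. Mean 12 gives at most 2.5% and about 3%. The fall is positive in every scenario.

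**Step 3, does the planned model help?** Applied to change from Run-In, a mixed model with treatment, sequence, period and random subject (stratum omitted) gives favourable rates of 23-36%, 8-10% and about 4%. It does not remove the bias.

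**Step 4, daytime restriction.** Criterion 7 counts CGM events at any hour, while the endpoint counts 8am-10pm. If 60-75% of events are diurnal at random (assumed), the percentage fall is unchanged. The favourable rate at mean 2 drops to about 16-31%.

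**Step 5, the randomized contrast.** Under the same selection, 45 mg BID versus 90 mg QD is rejected in 4-5% of trials (two-sided), as it should be.

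**Step 6, testing the remedy.** Run-In time after the event that completes criterion 7 is free of the selection if the person's rate is stable (residual within 0.3%). The meal test spoils this unless handled. Study Schedule and Mixed Meal Tolerance Test put one on Day 14 of every period, and no CGM removal is listed before the Run-In meal. If 7 Run-In days remain and the meal produces an event with probability 0.6 (assumed), it adds 0.6 × 14/7 = 1.2 events per 14 days to the Run-In rate but only 0.6 to each treatment period. With stable rates and meal-event probability 0.6-0.9, the spurious fall is 11-19%, 5-9% and 2-3% at means 2, 4 and 8. It vanishes when the meal window is dropped from every period.

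**The case against.** The strongest reply is that the threshold is low and these patients have many events. Introduction and Background speaks of frequent episodes, and criterion 6 requires a documented recurrent history. At a mean of 8 or more the bias is at most about 5%. This stands as a limit on size. It does not dispose of the point, because no Run-In rate or screen-failure figure shows where the trial lies.

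Second, the study is open-label, is described as preliminary (Rationale for Dose and Dose Regimen Selection) and uses nominal p-values. That argues for a modest remedy, but the plan still declares P<0.05 significant.

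Third, *baseline-adjusted* might mean Run-In as a covariate. The contrast between regimens would then be unaffected, as it already is. A p-value for each regimen against Run-In would still carry the bias.

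Fourth, the sensitivity analysis is imperfect. That is correct: it needs the meal-test exclusion, and it removes only part of the bias when rates vary between periods.

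**Conclusion.** The concern holds for the regimen-versus-Run-In comparison of CGM Level 2 event counts. The direction favours the drug provided that counts vary by chance within a person and the threshold excludes some candidates. The size rests on assumed rates: material if many candidates sit near the threshold, small if most are well above it.

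A reader might infer more than the documents support:

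- **That the trial's false-positive risk is 25-37%.** Those figures need a candidate mean near 2 and two required CGM events, with about half or more of candidates failing. The documents neither state nor exclude this.
- **That an observed fall would be artefact.** Only part of it would be, and the part is unknown.
- **That every endpoint is equally biased.** The Level 3 rate is selected on directly only if Level 3 events count toward criterion 7, which is unclear. SMBG rate, percent time below 54 mg/dL and meal-test nadir are affected only as far as they correlate with the qualifying events.
- **That the dose-regimen comparison is compromised.** It is not: both periods follow selection and their order is randomized.

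**What to change.** In Primary Efficacy Endpoint:

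1. Keep the change from the full Run-In, with its confidence interval, as the primary estimate. State that it is uncontrolled and subject to regression to the mean. Replace the significance rule so that P<0.05 on this contrast is not by itself evidence of a drug effect.
2. Add a sensitivity analysis of diurnal CGM event counts using only Run-In events and CGM hours after the event that completes criterion 7. Compare within participant, with an exposure weight or a log-exposure offset. Exclude the Day-14 meal-test window from Run-In and both treatment periods. State that it removes the bias only if each participant's rate is stable. With period variation about 12-14%, 8-10% and 5-6% remains at means 2, 4 and 8, which at mean 8 is no better than the plan. It does not address open-label reporting or the fixed time order.
3. Time-stamp the qualifying events, and reconcile *severe* in criterion 7 with the Level 2 and Level 3 wording in Screening Procedures and Secondary Endpoints. Report the number screened, the failures on criterion 7 and the distribution of Run-In counts, so that readers can bound the bias.

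Design, primary baseline and model stay. The costs are a more guarded claim and an imprecise sensitivity analysis. With a two-event threshold, standard errors rise about 20-43%, mean Run-In exposure is 7-10 days and 3-12% of participants keep under 2 days, before the meal window is removed.

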### **Exclusion Criteria**

Patients meeting any of the following criteria will be excluded from the study.

#### ***General Exclusions***

1. Use of an investigational drug within 5 half-lives of the study drug before Screening.
2. Donation or loss of >500 mL of blood or blood product within 56 days before the first dose of study drug.
3. Clinically significant active infection within 14 days before the first dose of study drug.
4. Any clinically relevant acute or chronic psychiatric, renal, hepatic, pancreatic, cardiovascular, neurological, hematological, or gastrointestinal abnormality (eg, inflammatory bowel disease) or active malignancy.
5. Major surgery within 6 months before randomization.
6. History of or current insulinoma or other cause of endogenous hyperinsulinism other than HH (e.g., insulin autoimmune hypoglycemia). Such causes must be ruled out if clinically suspected by the Investigator.

#### ***Exclusions Based on Laboratory Values***

7. Abnormal laboratory values of clinical significance as assessed by the Investigator. Note:

#### ***Exclusions Based on Recent or Concomitant Medication or Drug Use***

8. Use of agents that may interfere with glucose metabolism within 5 half-lives, as follows:
  - a. Anti-hyperglycemic agents (eg, insulin, sulfonylureas, meglitinides, metformin, thiazolidinediones [TZDs], dipeptidyl-peptidase [DPP-4] inhibitors, sodium-glucose-linked transporter 2 [SGLT2] inhibitors, GLP-1 agonists).
  - b. Alcohol (eg, beer, wine, drinks containing distilled spirits)
  - c. Fluoroquinolone antibiotics (eg, ciprofloxacin, gemifloxacin, levofloxacin, moxifloxacin, norfloxacin, ofloxacin)
  - d. Tramadol (chronic use of other opioids is permitted as long as dose remains stable throughout study)
  - e. Current use of acarbose, verapamil, diazoxide and or somatostatin analogs (eg. octreotide, pasireotide, lanreotide)

f. Systemic or inhaled glucocorticoids (eg, prednisone, prednisolone, methylprednisolone, beclomethasone, betamethasone, dexamethasone, hydrocortisone, triamcinolone) with exception of topically or nasally administered steroids

### **Subject Restrictions**

Participants must report any new prescription medications or over-the-counter preparations or any changes to concomitant medications to study staff for the duration of study participation

## **INVESTIGATIONAL PRODUCT, DOSAGE AND ADMINISTRATION**

Avexitide injection is a sterile, clear, colorless solution and is supplied in single-use 3 mL vials containing 0.5 mL solution. The drug product composition consists of 90 mg/mL avexitide injection (active ingredient). The avexitide investigation product should be stored refrigerated between 2°C to 8°C (35.6°F to 46.4°F), inclusive.

### **Dispensing and Administration of Study Drug**

Three kits of study drug (two containing 28 x 3mL vials and one containing 6 x 3mL vials of 90 mg/ml solution) will be dispensed by the Investigator on V4. Participants will be given written and oral instructions on how to store, draw up and safely administered study drug. The study drug will be administered as subcutaneous injections either once daily in the morning (90 mg QD), or twice daily (45 mg BID): once in the morning and the second daily dose approximately 12 hours later. During once daily dosing, the morning dosing will occur at least 60 minutes prior to the first morning meal. During twice daily dosing, the morning dosing will not be relative to the timing of the first meal of the day.

### **Missed Doses**

If patients miss a dose or a dose is delayed, the dose should be taken as soon as the missed or delayed dose is noted. In the event a dose is missed and it is time for the next dose to be taken, the missed dose should be taken along with the scheduled dose. However no more than 3 doses should be administered within any given 24-hour period.

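### A single missed-dose rule, limited only by number of doses, tells a once-daily participant to inject 180 mg at once, twice the largest planned single dose

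*Combined protocol and SAP*

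**What the plan says.** Dispensing and Administration of Study Drug sets the two regimens. Injections are given "either once daily in the morning (90 mg QD), or twice daily (45 mg BID"), the twice-daily schedule being "once in the morning and the second daily dose approximately 12 hours later". Rationale for Dose and Dose Regimen Selection describes both as a "90 mg total daily dose administered as 45 mg BID and 90 mg QD".

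Missed Doses applies to both without distinction. A missed or delayed dose is taken when it is noticed. If the next dose is already due, "the missed dose should be taken along with the scheduled dose". The one limit follows: "However no more than 3 doses should be administered within any given 24-hour period". No limit is given in mg, and there is no exception for the once-daily regimen.

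The product is "supplied in single-use 3 mL vials containing 0.5 mL solution", at 90 mg/mL. Dosing is at home by self-injection (Study Design). Adherence is estimated from returned vials, collected at the final visit (Drug Accountability; Appendix A).

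**The concern.** The two regimens have the same daily total, but their single doses differ twofold. A rule that counts doses therefore does different things in each. Under BID it brings the participant up to a single dose the trial already plans. Under QD it instructs a single injection that no part of the plan describes or justifies.

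Three things are at stake.

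- **Participant exposure.** Someone who follows the protocol exactly can self-administer, at home, twice the highest planned single dose.
- **Safety attribution.** The trial evaluates safety and tolerability of 45 mg BID and 90 mg QD in up to 20 participants. Appendix A shows no visit between day 1 and day 14 of Treatment Period 1, and none in Treatment Period 2 before day 14. The eDiary items listed under eDiary and Glucometer and under Dietary Treatment do not include the time or amount of injections. These may be recorded elsewhere, but the protocol does not say so. An adverse event after 180 mg could be counted against 90 mg QD.
- **The meal test.** If the day-13 QD dose is the one missed, the rule places 180 mg at the day-14 clinic visit, 90 minutes before the meal that yields the glucose-nadir secondary endpoint.

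**Working it through.** **Inputs.** Concentration 90 mg/mL and fill volume 0.5 mL (Investigational Product, Dosage and Administration). Scheduled dose 90 mg QD or 45 mg BID; kits of 28, 28 and 6 vials (Dispensing and Administration of Study Drug). Make-up rule and three-dose cap (Missed Doses). Earlier Phase 2 doses of 30 mg BID and 60 mg QD (Rationale for Dose and Dose Regimen Selection).

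**The plan's own figures reproduce.**
- Drug per vial: 90 mg/mL × 0.5 mL = 45 mg.
- QD: 90 / 45 = 2 vials a day. BID: 1 vial twice a day = 2 vials a day.
- Per 14-day period: 14 × 2 = 28 vials, matching each 28-vial kit.
- Dispensed: 28 + 28 + 6 = 62, against 56 needed for two periods, leaving 6 spare.

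**The make-up rule by regimen**

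| | 45 mg BID | 90 mg QD |
|---|---|---|
| Scheduled single dose | 45 mg (1 vial, 0.5 mL) | 90 mg (2 vials, 1.0 mL) |
| Missed + scheduled, taken together | 45 + 45 = 90 mg (2 vials, 1.0 mL) | 90 + 90 = 180 mg (4 vials, 2.0 mL) |
| Ratio to largest planned single dose (90 mg) | 90 / 90 = 1 | 180 / 90 = 2 |
| Ceiling implied by three doses in 24 h | 3 × 45 = 135 mg | 3 × 90 = 270 mg |

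The cap does not prevent the 180 mg injection, because two doses are within three. The yardstick here is the largest planned single dose. Make-up dosing exceeds the planned 90 mg daily total under BID as well.

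**Comparison with the earlier trial.** The cited Phase 2 study was one "evaluating two dosing regimens (30 mg BID and 60 mg QD) in 18 patients", so its largest single dose was 60 mg and 180 / 60 = 3. Introduction and Background cites other avexitide studies without giving their doses, so prior human exposure at 180 mg cannot be judged from the document.

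**Total drug.** Over two QD days, on time: 90 + 90 = 180 mg. Missed then doubled: 0 + 180 = 180 mg. The total is the same and only the peak differs.

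**Visibility in the vial count.** A 14-day QD period taken on time uses 14 × 2 = 28 vials. With one dose missed and then doubled: 12 × 2 + 0 + 4 = 28 vials. The count cannot tell them apart.

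**Occasions.** Doses 2 to 14 of the QD period can each be doubled, which is 13 occasions. Dose 14 is given in clinic, so 13 − 1 = 12 are at home. These are opportunities, not expected events.

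**Late doses.** A QD dose remembered at 23 h, followed by the next at 24 h, gives 180 mg within 1 h. Banning simultaneous doses is therefore not enough without a minimum interval. If a late dose is allowed only up to 12 h, the shortest gap is 24 − 12 = 12 h and the largest single administration is 90 mg.

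**The case against.** **No harm or breached limit is shown.** This stands. The document sets no single-dose ceiling, and the 90 mg yardstick is a reviewer's choice. Introduction and Background reports that avexitide was well tolerated in the earlier Phase 2 trial, though at lower doses. The point rests on an unplanned and unjustified peak, not on demonstrated toxicity.

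**The trigger is narrow.** Also true. The first instruction is to take a missed dose once noticed, so 180 mg at one time requires a QD dose left untaken for a full day. But that is the very case the second instruction was written to cover.

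**A dose might mean one 45 mg vial.** The cap would then be 135 mg in 24 hours and would block 180 mg. Missed Doses does not define the term, but Dispensing and Administration uses it for a scheduled administration (the twice-daily wording quoted above). On the vial reading, the cap would also forbid what the preceding sentence tells a QD participant to do. The reading fails, and a definition would still be needed.

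**The consequences may be caught in practice.** Staff review adverse events at Visits 5, 6 and 7, and are well placed on day 14 to notice a missed day-13 dose. Participants also receive instructions: "Participants will be given written and oral instructions on how to store, draw up and safely administered study drug". Those instructions are not in the file and may be specific to the regimen. This lowers the likely impact, but the protocol gives staff no different rule to apply. The meal-test scenario bears on one secondary endpoint; no effect on the primary CGM endpoint is shown.

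**Preserving total dose is a defensible aim.** It is, and dropping some QD doses while making up all BID doses treats the regimens unequally. That is a real cost of the change.

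**Conclusion.** The concern holds. Followed as written, the rule has a QD participant inject 180 mg at once, twice the largest planned single dose, whenever a dose is still untaken as the next falls due. Under BID the same words give 90 mg, which the plan already uses. The conclusion assumes that a dose means a scheduled administration and that no stricter instruction exists outside the file.

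What is established is an instructed, unsupported peak that the vial count cannot reveal. Harm, frequency and any effect on the trial's conclusions are not established. It should be fixed because it concerns participant safety and the attribution of adverse events to a regimen, and because the correction is cheap. Confidence is medium.

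**What to change.** State the rule by regimen, in both the protocol and the participant instructions.

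- **BID:** keep the present make-up rule, at most three doses (135 mg) in 24 hours.
- **QD:** take a late dose when noticed only if a stated minimum interval remains before the next scheduled dose; otherwise skip it. Twelve hours is an example, chosen because it is the shortest interval already planned (BID). The sponsor should confirm it from PK data.
- **Both:** never more than 90 mg (2 vials) in one administration.
- **Recording:** enter the time and number of vials of each injection in the eDiary.

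The fix has a limit: 180 mg in 24 hours stays possible under QD, but, with the 12-hour example, only as two 90 mg doses at least 12 hours apart.

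The cost is protocol wording, the instruction sheet and one eDiary item. Sample size, visits and drug supply are unaffected. A few missed QD doses would stay missed, slightly lowering QD exposure in those participants relative to BID; the injection record would show when this happened.
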